4.6 Methods To Be Used For Handling Missing Data

Missing data will not be imputed

5. Study Patients

5.1 Disposition of Patients

The number of patients in the ITT population will be presented by phase, dose level and overall.

The number of screened patients and the number of screen failure patients with their reason(s) of screening failure will be displayed.

The frequency of discontinuation from monalizumab treatment, of discontinuation from ibrutinib treatment and from study will be given for each phase, dose level and overall. The primary reason for discontinuation will be summarized. The details of the 'other reason' will be included in a listing.

5.2 Protocol Deviations

Major protocol deviations will be summarized for the ITT/safety population. Deviations to the protocol will be classified as major or minor by Innate pharma in a list sent to before database lock.

5.3 In- and Exclusion Criteria

Listing of all in- and exclusion criteria not met will be provided.

6. Demographic and other Baseline Characteristics

Descriptive statistics with respect to patient characteristics at baseline will be displayed for the ITT/safety population.

The variables to be summarized are:

- Sex, age, race and ethnicity
- Height, weight and BMI
- Cancer history
 - Time between initial diagnosis of CLL and date of first administration of study drug (in Months)

TPL Version: 02

Page 16 of 26

TPL N°: eTPL SA-02-01
Of SOP SA-02.08
TPL Effective Potes 31 Mar 2016

TPL Effective Date: 31 Mar 2016 Approved in Vault: 3/8/2019

- Number of previous line(s) of systemic CLL Treatment
- Presence of CLL abnormalities (yes, no or unknown) and type of genetic abnormalities of CLL at the time of diagnosis of CLL
- IGHV gene mutation (mutated, un-mutated or unknown) and ZAP 70 expression (positive, negative or uncertain/unknown) at the time of diagnosis of CLL
- Last line of previous systemic CLL treatment
 - \circ $\,$ The reasons for this treatment line will be displayed by the categories specified in the CRF
 - The IWCLL status before this CLL treatment and the progression status before CLL treatment will be displayed
 - o The number of cycles as well as the type of treatment will be displayed
 - The IWCLL best response to the induction will be summarized. If any maintenance/consolidation/intensification treatment was given, the IWCLL best response to this treatment will be displayed. And if any autologous transplant was performed, the IWCLL best response to this treatment will be displayed.
- CLL status at screening
 - Rai stage (0, I, II, III or IV)
 - o Disease status (Relapse CLL, Refractory CLL or previously untreated CLL)
 - Time between the date of diagnosis of the current CLL progression and the date of first administration of study drug (in Months)
 - For patients with relapse CLL: IWCLL status and progression status before CLL treatment
 - For patients with relapse CLL or previously untreated CLL: the reasons for giving the study drug treatment will be displayed by the categories specified in the CRF
 - Presence of CLL abnormalities (yes, no or unknown) and type of genetic abnormalities of CLL at screening
 - o IGHV gene mutation (mutated, un-mutated or unknown) and ZAP 70 expression (positive, negative or uncertain/unknown) at screening
- Bone marrow examination
 - Bone marrow aspirate: the quality of this sampling, the normocellular status for age, the cellularity status and the percentage of nucleated cells for lymphocytes will be summarized
 - Bone marrow biopsy: the quality of this sampling, the normocellular status for age, the cellularity status, the percentage of nucleated cells for lymphocytes (by the categories specified in the CRF), the presence of nodules and the main composition of these nodules will be summarized
- Medical history will be tabulated by system organ class and preferred term with four separate tables for 'ongoing' and 'not ongoing' and for related and not related to CLL.
- ECOG performance status
- Baseline laboratory serology results: HIV, HCV, Hbs antigen and Hbs antibody
- Child-bearing potential (yes or no, and reason for non-child-bearing potential), contraception practice and pregnancy test result.

7. Prior and Concomitant Treatment and procedures

The number and percentage of participants receiving a prior or concomitant medication will be displayed by ATC level 4 and first Anatomical Therapeutic Chemical class (ATC 1) for the ITT/safety population. Prior medications are the medications that

Page 17 of 26

TPL N°: eTPL SA-02-01 Of SOP SA-02.08 TPL Effective Date: 31 Mar 2016

Version: 2.0

started and stopped before the date of first administration of the study drug. The concomitant medications will be grouped in two categories. The first group of concomitant medications corresponds to the medications which started before the date of first administration of study drug and which stopped on or after this date. The second group of concomitant medications corresponds to the medications which started on or after the date of first administration of study treatment and which stopped on or after this date. The medications with missing start and end dates will be classified in this last category. The prior medications and the two groups of concomitant medications will be displayed in three separate tables.

Concomitant procedures and surgeries will also be tabulated by system organ class and preferred term for the ITT/safety population.

8. Efficacy Evaluation

All the efficacy analyses are performed on both phases of the trial. The rates of remission (\S 8.1-8.4) will be assessed using the main endpoint population. The survival endpoints (\S 8.5) will be assessed in the ITT/safety population.

8.1 Rate of complete remission

In both phases, the rate of complete remission is assessed 52 weeks after the initiation of combined treatment

The rate of complete remission (CR) will be calculated in the main endpoint population (see §4.2.2). Within this population, the CR rate will be computed as the number of patients with a confirmed complete remission at W52 divided by the total number of patients in the main endpoint population.

The rate of complete remission with 95% confidence interval will be summarized overall and in the subgroup treated at the RP2D.

In order to claim a CR, the CR must be confirmed. In order to have a confirmed CR (cCR), the CR must be confirmed by a scan and a bone marrow assessment assessed at least 2 months after the first occurrence of CR.

8.2 Rate of overall and partial remission

The rate of overall and partial remission is assessed 52 weeks after the initiation of combined treatment and during the in-study follow-up.

The rates of overall (i.e cCR, uCR or PR) and partial remission (PR) will be calculated in the main endpoint population (see §4.2.2). Within this population, the overall/partial remission rates will be computed as the number of patients with a any/partial remission at W52 divided by the total number of patients in the main endpoint population.

The rate of overall (and partial) remission will be summarized overall and by dose level and the 95% confidence interval for this rate will be calculated only overall and in the subgroup treated at the RP2D.

The Best Overall Response (BOR) of each patient will be displayed in a summary table. The BOR is the best response (i.e cCR, uCR, PR, SD, PD or NE) taking into account all assessment results until the last disease assessment. The PR does not need to be confirmed and there is no minimum duration for SD. However, a listing with all the derived BOR will be sent to the Sponsor for medical review before the database lock.

Page 18 of 26

TPL N°: eTPL SA-02-01 Of SOP SA-02.08 TPL Effective Date: 31 Mar 2016 TPL Version: 02
Approved in Vault: 3/8/2019

The evolution of tumor response over time will be displayed, separately by patient, via a Swimmer plot (an example of swimmer plot can be found on page 2 of the following document:

Version: 2.0

https://www.pharmasug.org/proceedings/2014/DG/PharmaSUG-2014-DG07.pdf).

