# 3.1.2 Secondary endpoints

Part 1: phase lb

0

Secondary endpoints are:

- Rate of overall and complete or partial response defined according to the IWCLL guidelines with an additional category of "PR with lymphocytosis" achieved with IPH2201 given as a single agent during 2 cycles, and, thereafter, with the combination of IPH2201 and ibrutinib, and assessed 52 weeks after the initiation of the combined treatment and during the in-study follow-up period.
- Duration of response, PFS and OS. Progression is defined according to the IWCLL guidelines
- with the exception that lymphocytosis cannot be used as the sole criterion for disease progression
- Pharmacokinetic endpoints
  - Concentration at the end (Cinf end) of the 1st to 4th administrations of IPH2201 (every 2 weeks) and thereafter, every at the end of every other administration (every 8 weeks)
  - Accumulation index in terms of Cmax ratio, between 1st administration and selected later administrations
  - Area under the curve from 0 time to 14 days at the 1st (IPH2201 administered alone) and 3rd (IPH2201 and ibrutinib) administrations for patients in the dose escalation phase

CONFIDENTIAL

[figure not shown]
Release date: Edition number

MOD-3783

12 August 2016

GED version

Terminal half-life (T1/2) and clearance (CL) for patients who will complete the study

Secondary endpoints are:

- Rate of complete response defined according to the IWCLL guidelines, documented during the in-study follow-up period of the study.
- o Rate of overall and partial response defined according to the IWCLL guidelines with an additional category of "partial response with lymphocytosis"
- 0
- o Duration of response, progression-free survival (PFS) and overall survival (OS); progression is defined according to the IWCLL guidelines with the exception that lymphocytosis cannot be used as the sole criterion for disease progression
- o Safety of IPH2201: will be assessed using the CTCAE version 4.03 (descriptive analysis of frequency and severity of adverse events); related adverse events followed to resolution (grade ≤ 1) unless deemed irreversible. Safety evaluation will also be based on clinical laboratory tests collected to assess lab abnormalities, as well as results of vital sign

measurements, electrocardiograms (ECGs), physical examinations and imaging studies.

The following endpoints are optional in the phase IIa part of the study

- Pharmacokinetic endpoints

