#### Week 6 day 1 (W6)

The following pre-dose assessments must be done prior to IPH2201 and ibrutinib administrations:

- Concomitant illness / Concomitant medication
- Safety assessments as following:
  - o Vital signs (including weight)
  - Physical examination, focused on symptoms and new findings (from screening visit)
  - o ECOG status
  - Adverse events
- Pre-dose Safety laboratory (H0)
  - o Biochemistry
  - o Hematology
  - o A 12-lead ECG
- Pre-dose PK/PD assessments (H0)
  - o PK
  - 0

IPH2201 administration should be performed 14 days +/- 3 days after the previous administration.

Release date: Edition number 12 August 2016 MOD-3783

GED version

IP2201 will be administered first, followed by ibrutinib, to be taken after the end of IPH2201 perfusion.

- The following post-dose assessments are required at W6 visit:
  - PK assessments at H0+1 (at end of the 1-hour infusion of IPH2201)

### 6.2.2.5 Cycle 5 to cycle 15

From cycle 5 (W8) cycles last for 4 weeks and consist of 1 dosing visit only.

The following pre-dose assessments should be done prior to IPH2201 and ibrutinib administrations:

- Concomitant illness/Concomitant medication
- Tumor assessment:
  - a tumor assessment by physical examination is required at all dosing visits starting from W8 visit (monthly assessments);
  - a CT-scan should be performed at W16 and at any other visit to confirm a CR or progression, whenever one of these events is suspected
- Safety assessments
  - Vital signs (including weight)
  - o Physical examination, focused on symptoms and new findings (from screening visit)
  - o ECOG status
  - Adverse events
  - A 12-lead ECG is required at W16 and W32
- Pre-dose Safety laboratory (H0)
  - Hematology: RBC, WBC with differential count, platelets, hemoglobin; MCV and hematocrit
  - Biochemistry: sodium, potassium, chloride, bicarbonate, calcium, magnesium, phosphate, total proteins, and albumin, urea, uric acid, creatinine, calculated creatinine clearance, ALP, total bilirubin, LDH, AST (SGOT), ALT (SGPT), GGT, amylase, lipase, glucose, CRP and fibrinogen, required at W16, W24, W32, W40 and W48
  - o Urinalysis at predose of W32
- Pre-dose PK/PD assessments (H0)
  - o Pharmacokinetics at W12, W20, W28, W36 and W44

- Testing for IgG, IgM, IgA and total immunoglobulin levels in predose of W16 and W32
- Other specific assessments (H0)

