3.1.2.2 Secondary Objectives

The secondary objectives are

- To document the anti-leukemic activity of the combination of monalizumab and ibrutinib. This corresponds to the analysis of the following endpoints:
 - Rate of complete response defined according to the IWCLL guidelines, documented during the in-study follow-up period of the study
 - Rate of overall and partial response defined according to the IWCLL guidelines with an additional category of "partial response with lymphocytosis"
 - Quantitative changes of the CLL clone in the peripheral blood and the rate of response with undetectable MRD in peripheral blood and bone marrow of patients in CR (immune-phenotype by flow cytometry)
 - Duration of response, PFS and OS. Progression is defined according to the IWCLL guidelines with the exception that lymphocytosis cannot be used as the sole criterion for disease progression
- To assess the safety of the combination of monalizumab and ibrutinib. This corresponds to the analysis of adverse events, laboratory abnormalities, as well as results of vital sign measurements, electrocardiograms (ECGs), physical examinations and imaging studies.

TPL N°: eTPL SA-02-01 TPL Version: 02 Of SOP SA-02.08 TPL Effective Date: 31 Mar 2016 Approved in Vault: 3/8/2019

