8.4 Remission with undetectable MRD

Undetectable MRD is defined as the percentage of CLL cells of all lymphocytes below 0.01%. The rate of patients in cCR at W52 with undetectable MRD in peripheral blood and bone marrow will be summarized overall and by dose level, and the 95% confidence interval for this rate will be calculated only overall for the patients in the phase Ib and for the patients in the phase IIa. Remission with undetectable MRD needs to be confirmed, i.e. CR and undetectable MRD should be met jointly and confirmed jointly. The rate of remission with undetectable MRD in peripheral blood and in bone marrow will be displayed separately.

8.5 Duration of Remission (DOR), Duration of Complete Remission (DOCR), Progression free Survival (PFS) and Overall Survival (OS)

The duration of Remission (DOR) and duration of complete Remission (DOCR) will be assessed in the main endpoint population, whereas the Progression Free Survival (PFS) and Overall Survival (OS) will be assessed in the ITT/safety population.

The DOR, for the remission assessed at 52 weeks, is defined as the time from the date of first evaluation of the remission (CR or PR) to the first documentation of progressive disease, relapsed disease or death. In case an assessment of a progressive disease, relapsed disease or death record does not exist, the duration of remission is censored at the time of the last disease assessment date. The duration of remission is only calculated for the patients with a cCR, an uCR or a PR assessed at 52 weeks.

The DOCR is calculated similarly for the patients with a cCR assessed at 52 weeks.

The PFS is defined as the time from first dose administration until the occurrence of progressive disease, relapsed disease or death from any cause. Patients without an event at the time of the analysis will be censored at his or her last disease assessment date; patient with no post-baseline assessments will be censored at the day of first dose administration.

The OS is defined as the time from first dose administration until death from any cause. Alive Patients are censored at the most recent date they are known to be alive. Subjects with no assessment post-baseline will be censored at the day of first dose administration.

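### SAP 8.2 and 8.5 leave out the promised category of partial response with lymphocytosis, and the protocol's progression rules omit the matching lymphocytosis exception

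*SAP*

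**What the plan says.** The promise is made in both documents. For phase Ib, protocol 3.1.2 lists as a secondary endpoint "Rate of overall and complete or partial response defined according to the IWCLL guidelines with an additional category of" PR with lymphocytosis (PR-L below). For phase IIa, SAP 3.1.2.2 has "Rate of overall and partial response defined according to the IWCLL guidelines with an additional category of" the same kind of response, and SAP 3.1.1.2 repeats it for phase Ib. The same lists say that lymphocytosis cannot be the only ground for calling progression when duration of response and PFS are analysed.

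The analysis sections do not follow through.
- Overall remission, SAP 8.2: "The rates of overall (i.e cCR, uCR or PR) and partial remission (PR) will be calculated in the main endpoint population".
- Best overall response (BOR), SAP 8.2: "The BOR is the best response (i.e cCR, uCR, PR, SD, PD or NE) taking into account all assessment results".
- DOR, SAP 8.5: it runs from "the time from the date of first evaluation of the remission (CR or PR"), and "The duration of remission is only calculated for the patients with a cCR, an uCR or a PR assessed at 52 weeks".

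PR-L appears in none of these lists, nor anywhere else in the visible text of SAP section 8.

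Protocol 7.2.1 names PR-L in its heading, but the criteria below it describe PR only and include a fall of at least 50% in blood lymphocytes. Appendix III grants PR on any two group A criteria plus one group B criterion. Protocol 7.2.2 lists a 50% lymphocyte rise, with at least 5000 B lymphocytes per microlitre, among events of which one suffices for progression.

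**The concern.** Lymphocytosis on ibrutinib is foreseeable. Protocol 1.1.5 describes redistribution lymphocytosis as a recognised effect of this drug class that is not progression. Protocol 1.1.5.1 reports that 15-20% of refractory patients on ibrutinib alone had a PR with lymphocytosis, over and above a 71% response rate. Every patient here is planned to receive ibrutinib.

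Two things are at stake. First, a response category promised as part of a secondary endpoint would not be reported. Without a written rule, whether such a patient is PR or SD, and when the remission began, would be settled after responses are known in an open-label trial. Second, a site that applies the progression text in 7.2.2 literally would have to stop treatment, under 3.5.1, for an effect that the protocol's own background says is not progression.

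**Working it through.** **1. The plan's own figure.** The phase IIa design (SAP 3.3.2) has n = 27, p0 = 0.05, p1 = 0.20, one-sided alpha 0.05 and power 0.80, and is positive with at least 4 CRs. The exact probability is P(X ≥ 4) = 1 − Σ(k = 0 to 3) C(27,k) p^k (1 − p)^(27−k).
- At p = 0.05: 0.0437.
- At p = 0.20: 0.8177.
- No smaller n in the range searched (20 to 34) meets both limits.

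The design reproduces. PR-L does not enter it, because CR requires blood lymphocytes below 4 × 10⁹/l (protocol 7.1).

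**2. One patient under each rule.** Take a patient whose nodes and spleen have each shrunk by at least 50%, whose platelets exceed 100,000/µL, and whose lymphocytes have not fallen by 50%.
- Criteria listed in 7.2.1: the lymphocyte item is missed, so not PR. If there is no progression either, SD.
- Appendix III: two group A criteria and one group B criterion are met, so PR.
- 7.2.1 heading: PR-L is an addition under partial response, so a form of PR.
- SAP 3.1: a category in its own right.
- SAP 8.2: no PR-L entry, so the patient must be coded as something else.

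If the lymphocytes have risen by 50% or more, the Appendix III progression row is met as well. In 7.2.2 the same holds once there are at least 5000 B lymphocytes/µL. Only the exception in protocol 3.1.2 and SAP 3.1 prevents that label.

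**3. Start of DOR.** SAP 8.5 dates DOR from the first CR or PR. A patient who is PR-L first and conventional PR later has two candidate start dates, depending on whether PR-L counts as PR. This applies even if the lymphocytosis has cleared by week 52.

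**4. Size per patient.** With 27 patients in the denominator, each PR-L patient changes overall response by 1/27 = 3.7 percentage points. SAP 8.2 also says "The rate of overall (and partial) remission will be summarized overall and by dose level". In a phase Ib level of 3 to 6 patients, one patient is worth 1/6 = 17 to 1/3 = 33 points, which reflects cohort size and not anything special to PR-L.

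**5. Upper illustration.** This assumes that the background rates for ibrutinib alone hold for 27 patients at week 52, which no document states.
- Conventional response: 0.71 × 27 = 19.2, taken as 19. 19/27 = 70.4% (exact 95% CI 49.8 to 86.2).
- PR-L: 0.15 × 27 = 4.05 and 0.20 × 27 = 5.4, taken as 4 and 5.
- PR-L counted: 23/27 = 85.2% (66.3 to 95.8) to 24/27 = 88.9% (70.8 to 97.6).

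**6. Progression rules side by side.**
- Protocol 3.1.2 and SAP 3.1: lymphocytosis alone is not progression.
- Protocol 7.2.2 and Appendix III: a lymphocyte rise can suffice, with no exception stated.
- Protocol 4.3: withdrawal on IWCLL 2008 progression, no exception stated.
- Protocol 3.5.1: treatment stops on progression.

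**The case against.** The strongest reply is that the documents, read together, already answer the question. SAP 3.1 ties PR-L to overall and partial response, the 7.2.1 heading places it under PR, and Appendix III reaches PR without a lymphocyte fall. On that reading PR-L is coded PR, overall response and DOR already include it, and only its separate display is missing. This carries weight as the more natural reading. It does not remove the lymphocyte criterion listed in 7.2.1, and it does not supply the separate category. The sponsor's review of BOR before lock, the patient listings and the swimmer plot would make such cases visible, but they contain no rule.

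A reader might take 70% versus 85-89% as the expected distortion. The documents do not support that. The contrast arises only if PR-L is excluded from PR, and it borrows rates from ibrutinib alone in refractory disease with no time point. The trial also enrols untreated patients, and no week-52 PR-L frequency is given. It is an upper illustration at most.

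A reader might also turn the visit schedule into a DOR error of so many weeks, since "a tumor assessment by physical examination is required at all dosing visits starting from W8 visit" (protocol 6.2.2.5). That concerns physical examination. In trials 7.2.1 judges nodal response by CT, and routine CT after baseline is at W4, W16 and end of study. No figure in weeks can be defended.

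Finally, the progression conflict is a matter of site conduct, separate from the SAP tables. That is correct, and it is judged separately below.

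**Conclusion.** The point holds for secondary, descriptive endpoints and should be corrected.

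**Response category.** The SAP as written does not deliver a category that both documents promise. The protocol's rules can classify the same patient as PR or SD, so BOR, overall response, entry to DOR and its start date can differ. The size is 3.7 percentage points of overall response per affected patient, assuming 27 patients in the main endpoint population. The number affected is unknown. If all PR-L is coded PR, the overall rate does not move, and what is missing is the separate row and the written rule.

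**Progression rule.** Protocol 7.2.2, Appendix III and 4.3 contradict the exception in 3.1.2. A reader might infer that the PFS analysis is wrong. The documents do not show this, because SAP 3.1 states the exception for that analysis. A reader might also infer that the CR rate is biased through patients withdrawn for lymphocytosis. Nothing shows that any site acted on 7.2.2 alone, and protocol 1.1.5 warns against it. What is shown is a conflict in the instructions to sites on stopping treatment, with no measurable effect.

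No decision rule uses overall response, BOR, DOR or PFS. The CR definition, the sample size and the 4/27 rule stand.

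**What to change.** - **SAP 8.2:** add PR-L as its own BOR category, defined as all PR criteria met except the lymphocyte fall. Count it in overall response and show it as a separate row, so that the rate without it can be read off.
- **SAP 8.5:** state that the first PR-L date starts DOR, list PR-L among the qualifying week-52 responses to match, and cross-refer progression to the exception in SAP 3.1.
- **Protocol 7.2.2, Appendix III and 4.3:** add that lymphocytosis alone is not progression.

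The SAP part costs some wording and one table row. It needs no new data, since blood counts with differential and tumour assessments are already scheduled. Whether the CRF response field offers PR-L is not shown; if it does not, PR-L can be derived from the recorded components. The protocol part changes a withdrawal rule and so needs an amendment with IRB approval (protocol 12.2). With last patient last visit planned for 1Q 2019 and the SAP stamped 3/8/2019, it may come too late to change much at sites. The SAP correction does not depend on it.
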